## I. LIST OF ABBREVIATIONS AND KEY TERMS

### List of Abbreviations

Abbreviations	Description of abbreviations
AE	Adverse Event
ADT	Androgen Deprivation Therapy
ALP	Alkaline Phosphatase
ALT	Alanine Aminotransferase
AR	Androgen Receptor
AS	Active Surveillance
AST	Aspartate Aminotransferase
BFI	Brief Fatigue Index
BMI	Body Mass Index
CBC	Complete Blood Count
CSR	Clinical Study Report
CT	Computerized Tomography
DHT	Dihydrotestosterone
ECG	Electrocardiogram
ECOG	Eastern Cooperative Oncology Group
eCRF	Electronic Case Report Form
EPIC	Expanded Prostate Cancer Index Composite
FAS	Full Analysis Set
FDA	Food and Drug Administration
GS	Gleason Score
IRT	Integrated Response Technology
ISN	International Study Number
LS	Least Square
MAX-PC	Memorial Anxiety Scale for Prostate Cancer
MedDRA	Medical Dictionary for Regulatory Authorities
MiPS	Michigan Prostate Score
MMRM	Mixed Model Repeated Measures
mpMRI	Multiparametric Magnetic Resonance Imaging
MRI	Magnetic Resonance Imaging
MUGA	Multi Gated Acquisition Scan
NCCN	National Comprehensive Cancer Network
NCI-CTCAE	National Cancer Institute Common Terminology Criteria for Adverse Events
PD	Protocol Deviation
PPS	Per Protocol Set
PSA	Prostate Specific Antigen
QOL	Quality of Life
SAE	Serious Adverse Event
SAF	Safety Analysis Set
SAP	Statistical Analysis Plan
SEER	Surveillance, Epidemiology and End Results
SF-12	Medical Outcomes Study 12-Item Short Form Survey
TEAE	Treatment-Emergent Adverse Event

Abbreviations	Description of abbreviations
TLFs	Tables, Listings and Figures
TRUS	Transrectal Ultrasonography
ULN	Upper Limit of Normal
WHO	World Health Organization

## **1 INTRODUCTION**

This Statistical Analysis Plan (SAP) contains a more technical and detailed elaboration of the principal features of the analysis described in the protocol, and includes detailed procedures for executing the statistical analysis of the primary and secondary endpoints and other data.

The SAP is finalized and signed prior to any of the following: study unblinding, database hard lock, interim analysis, or accumulation of a substantial amount of data to ensure lack of bias. If needed, revisions to the approved SAP may be made prior to database hard lock. Revisions will be version controlled.

This statistical analysis is coordinated by the responsible biostatistician of Astellas Pharma US, Medical Affairs, Americas. Any changes from the analyses planned in the SAP will be justified in the Clinical Study Report (CSR).

Prior to database hard lock, a final review meeting of data and tables, listings, and figures (TLFs) will be held to allow a review of the clinical trial data and to verify the data that will be used for analysis set classification. If required, consequences for the statistical analysis will be discussed and documented. A meeting to determine analysis set classifications may also be held prior to database hard lock.

### **1.1 Background**

Prostate cancer is the most commonly diagnosed cancer (other than skin cancer) among men. In 2015 the American Cancer Society estimates that 220,800 men will develop prostate cancer in the United States and about 27,540 will die of prostate cancer (American Cancer Society, 2015). Of those diagnosed, 80% will be diagnosed with localized disease according to Surveillance, Epidemiology and End Results (SEER) data (SEER 18 2005-2011). For localized disease, there are multiple options – active surveillance (AS), radical prostatectomy and external beam radiotherapy / brachytherapy (NCCN, 2015). Interventional options, however, carry risks. Radical prostatectomy (open or robotic) has long term risks of erectile dysfunction and urinary incontinence. External beam radiation therapy and brachytherapy also carry risks, such as erectile dysfunction, urinary incontinence and bowel complications. AS has emerged as one of the recommended options for localized prostate cancer (Mohler et al, 2010; Thompson et al, 2007). AS use is increasing for low risk disease over the years 2010-2013 compared to the years before then (Cooperberg & Carroll, 2015; Ritch et al, 2015; Weiner et al, 2015). Ritch et al (2015) also noted increasing use of observation for low risk prostate cancer in an analysis of the SEER-Medicare database. This increase in AS is mostly due to concern that clinically low risk prostate cancer is over-treated, and AS may reduce unnecessary treatment in these subjects. (Lane et al, 2014; Wilt, 2014; Wilt et al, 2012; Bill-Axelson et al, 2011). AS studies have also included men with higher risk features including Gleason pattern 4 (Klotz et al, 2015; Cooperberg et al, 2011).

[figure not shown]
Subjects who progress on AS are at risk for sequelae of their prostate cancer and often receive interventions which carry significant risks and side effects. To date, no studies have been published with an intervention of a known anti-cancer agent in an AS population.

Because of this, novel approaches are needed to both stratify and offer options for those on AS as well as to offer an intervention that might affect progression. Also, current AS groups

encompass different subject populations. Some populations with certain characteristics (related to medical or family history or ██████████ *CCI* ██████████ might progress more often on AS than other populations. This study will allow us to examine these issues, as well as to examine any effect of enzalutamide on these different subsets of subjects. The use of enzalutamide monotherapy will potentially allow for optimal tumor treatment without the side effects and effects on quality of life inherent to androgen deprivation therapy (ADT).

## 2 FLOW CHART AND VISIT SCHEDULE

**Figure 1 Flow Chart**

Abbreviations: AS = active surveillance, enz. = enzalutamide (160 mg PO daily), yr = year, m = months

**Table 2 Schedule of Assessments**

Study Visit Name	Screening	Randomization	3m	6m	9m	12m	15m	18m	21m	24m	>24m, q6m 	Unscheduled 
Study Day	-28 to -7	1	85	176	267	358	455	545	635	730	>730	n/a
Week	-4 to -1	1	13	26	39	52	65	78	91	104	>104	n/a
Window (days)			± 7	± 7	± 7	± 7	+7	+7	+7	+7	± 7	n/a
Informed Consent	X											
Medical History 	X		X 									
Inclusion/Exclusion Criteria	X		X									
Randomization		X										
Vital Signs	X		X	X	X	X	X	X	X	X	X	X
Physical Examination, Weight 	X			X	X	X	X	X	X	X	X	X
12-Lead ECG	X 											
MUGA/Echocardiogram 	X 											
Clinical Labs 	X		X	X	X	X	X	X	X	X	X	X
Serum hormone levels 		X			X				X			X
Serum PSA 	X		X	X	X	X	X	X	X	X	X	X 
Digital Rectal Examination	X			X		X		X		X		X 
Transrectal ultrasound-guided prostate biopsy(12 core) 	X 				X				X			X 
BFI 		X	X	X		X		X		X		
SF-12 		X		X	X		X		X		X	
EPIC 		X		X	X		X		X		X	
MAX-PC 		X		X	X		X		X		X	
Adverse Events 	X		X	X	X	X	X	X	X	X	X	X
Concomitant Medications	X		X	X	X	X	X	X	X	X	X	X
Therapies and Outcomes Review	X		X	X	X	X	X	X	X	X	X	X
Study Drug Dispensing 	X		X	X	X	X						
Blood Sample for Potential Future Analysis(optional) 	X		X	X	X	X	X	X	X	X	X	X

1. Subjects will be followed every 6 months until the last subject (study-wide) has completed the 24m Visit.
2. Unscheduled visits may be performed at any time during the study whenever necessary to assess for or follow-up on adverse events (AEs), at the subject's request or if deemed necessary by the investigator.
3. Medical history will include capturing information about any first degree relatives with prostate cancer. Any updates to the subject's medical history will be recorded at the Randomization Visit (Study Day 1) prior to randomization.
4. A complete physical examination will be completed at the Screening Visit. For all visits after the Randomization visit, only a brief physical examination is required.
5. This procedure (if required) must be done within 28 days prior to randomization.
6. A multi-gated acquisition (MUGA) scan or echocardiogram is only required if the subject has a history of anthracycline or anthracenedione (mitoxantrone) treatment.
7. Clinical labs, which will be assessed by the study's central laboratory, include serum chemistries (comprehensive metabolic panel) and hematology (CBC with differential).
8. Serum hormonal levels to be measured are testosterone, DHT, dihydroepiandrosterone, androstenedione and estradiol.
9. Serum PSA will be measured by the study's central laboratory.
10. If warranted per Investigator's clinical opinion or per standard of care.
11. [REDACTED] **CCI** [REDACTED].
12. Biopsies may be done with or without mpMRI targeting. Sites must use a consistent method (either with or without mpMRI targeting) for all of their study subjects. Any biopsy performed during the subject's study participation will be analyzed centrally (for histological reading, [REDACTED] **CCI** [REDACTED]).
13. Biopsy must be done within 6 months prior to the Screening Visit, and submitted for central analysis (histological reading, [REDACTED] **CCI** [REDACTED]). For this biopsy, a minimum of 10 cores is required.
14. Subjects who withdraw from the study prior to the 24m Visit will be asked to complete all subject reported outcomes questionnaires (BFI, SF-12, EPIC, MAX-PC) at their final study visit.
15. Only the urinary, sexual and hormonal domains will be used.
16. Adverse events (serious and non-serious) will be collected from the time the subject signs the consent form until the subject completes the study.
17. Study drug is only applicable to subjects randomized to the enzalutamide arm; subjects randomized to AS will not be dispensed any study drug.
18. Subjects will have the option of having an additional sample collected at each phlebotomy session for storage and analysis in future trials of future trials of biomarker discovery for localized prostate cancer

### **3 STUDY OBJECTIVE(S) AND DESIGN**

#### **3.1 Study Objective(s)**

The primary objective is to compare the time to prostate cancer progression (pathological or therapeutic progression) between subjects treated with enzalutamide versus subjects undergoing active surveillance.

The secondary objectives are to evaluate:

- Safety
- Proportion of subjects with negative biopsy for cancer at 1 year and 2 years
- Percent of cancer positive cores at 1 year and 2 years
- Time to PSA progression (secondary rise in serum PSA $\geq$ 25% above baseline or  $\geq$ 25% above nadir or absolute increase  $\geq$  2 ng/mL)
- Proportion of subjects with secondary rise in serum PSA $\geq$ 25% above baseline or  $\geq$ 25% above nadir or absolute increase  $\geq$  2 ng/mL at 1 year and 2 years
- Brief fatigue index (BFI)
- Medical outcomes study 12-item short form survey (SF-12)
- Expanded Prostate Cancer Index Composite (EPIC) questionnaire- urinary, sexual and hormonal domains
- Memorial Anxiety Scale for Prostate Cancer (MAX-PC) questionnaire

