**CCI**

#### **3.2 Study Design**

This is a multicenter, randomized, open label exploratory study, conducted in the US and Canada, evaluating the efficacy and safety of enzalutamide for extension of time to prostate cancer progression (pathological or therapeutic) in subjects with clinically localized, histologically proven prostate cancer that is categorized as low risk or intermediate risk and who are under AS. A total of 222 subjects from approximately 50 centers will be enrolled. Subjects are eligible if they were diagnosed within 6 months of screening and have been on AS. A minimum of ten cores from transrectal ultrasound-guided prostate biopsy (mpMRI targeted versus non-mpMRI targeted) are required; confirmatory biopsy before entering the study is not required and is done at the discretion of the investigator.

Low risk is defined as T1c-T2a, PSA $<$ 10, N0, M0 (or presumed N0, M0 if computerized tomography [CT]/bone scan not done due to low risk of metastases), GS  $\leq$  6, ECOG status  $\leq$  2 and estimated life expectancy  $>$  5 years. Intermediate risk is defined as T2b-T2c, PSA $<$ 20, N0, M0 (or presumed N0, M0 if CT/bone scan not done), GS  $\leq$  7 (3+4 pattern only), ECOG status  $\leq$  2 and estimated life expectancy  $>$  5 years.

Prostate cancer progression is defined as either therapeutic progression or pathological progression. Therapeutic progression is defined as the earliest occurrence of primary therapy for prostate cancer (prostatectomy / radiation / focal therapy / systemic therapy). Pathological progression is defined as increase in primary or secondary Gleason pattern by  $>$  1 or higher

proportion of cancer positive cores (>15% increase). Subjects will be stratified by low versus intermediate risk and type of biopsy performed (mpMRI targeted versus non-mpMRI targeted).

Subjects will be randomized (1:1) either to receive treatment with enzalutamide (160 mg), administered as four 40 mg capsules, by mouth, once daily or to AS during the one year study treatment period. Following the one year treatment period, all subjects will be followed for one additional year. Subjects will be followed up every 3 months for these 2 years, after which follow-up will either be every 6 months or unscheduled until the last subject finished their 2 year follow-up. Serum PSA will be measured at baseline and every 3 months during subsequent follow-up visits.

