## 6.4 Other Variables

To clearly state, the following variables are defined:

- Month = 30.4375 days. Year = 365.25 days.
- $BMI(kg/m^2) = Weight(kg) / Height(m^2)$
- Age at randomization=  $\text{floor}((\text{intck}(\text{'month'}, \text{birth date}, \text{randomization date}) - (\text{day}(\text{randomization date}) < \text{day}(\text{birth date}))) / 12)$
- Time since initial/histological diagnosis (years) =  $[(\text{date informed consent signed} - \text{date of initial/histological diagnosis}) + 1] / 365.25$ .
- Time since initial diagnosis to Randomization (years) =  $[(\text{date of Randomization} - \text{date of initial diagnosis}) + 1] / 365.25$ .
- The duration of treatment was calculated as the (last dose date – first dose date) + 1.
- Number of pills taken from one visit to the next = number of pills dispensed – number of pills returned.
- Study drug compliance at each visit is calculated as =  $[(\text{number of pills dispensed} - \text{number of pills returned}) / (4 * \text{number of days in the visit period})] * 100$ .
- Baseline results are defined as the last assessment prior to first dose of study drug, for subjects randomized to once daily enzalutamide. For subjects randomized to active surveillance, baseline is defined as the last assessment prior to or on the date of randomization.
- Treatment Emergent Adverse Events (TEAEs) are any AEs occurring on or after date of first study drug dose date (or randomization for AS) until 30 days post-treatment end date (or 1-year plus 30 days for AS).
- Treatment Phase is defined as date of first study drug dose (or randomization for AS) until either 30 days post treatment end date or (if earlier) study discontinuation date.
- 1-Year Follow-Up Phase is defined as 31 days post treatment end date until either completing 1-Year Follow-Up or (if earlier) study discontinuation date.
- Continued Follow-Up Phase is defined as the day after completing 1-Year Follow-Up phase until study discontinuation date.

Study Day is defined using the following step-wise function:

- If date of interest is on or following randomization, Study Day = Date of Interest – Randomization Date + 1;
- Else, Study Day = Date of Interest – Randomization Date.

Change from baseline is the difference between the result on a post baseline visit and baseline assessment.

Rise in serum PSA is defined as  $PSA \geq 25\% \text{ of baseline or } \geq 25\% \text{ above nadir or } \text{absolute increase} > 2\text{ng/mL}$ .

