### 7.4.1 Analysis of Primary Endpoint(s)

The primary efficacy endpoint is time to prostate cancer progression (pathological or therapeutic), and the hypothesis for analysis is:

$H_0$ : The time to progression for Enzalutamide and Active Surveillance (AS) are the

same  $H_1$ : The time to progression for Enzalutamide and AS are not the same

Median and 95% confidence intervals for time to prostate cancer progression (pathological or therapeutic) will be calculated with the Kaplan-Meier (KM) method for each treatment group. Subjects with no cancer progression at the time of trial completion, discontinuation or death will be censored at the last assessment date. Additionally, subjects switching therapy during the study will be censored at the time of the initial therapy switch, but subjects discontinuing therapy will not be censored until the time of study discontinuation. If less than 50% of subjects progress by study cut-off time, the 25th percentile and its two-sided 95% confidence interval will be reported. KM plots will be generated.

Treatment group differences between enzalutamide versus AS will be based on a Cox regression model. The resulting Hazard ratio (enzalutamide/AS) and 95% confidence interval will be included in the summary. Censoring assumptions will follow the same rules as applied for the KM estimates. Fixed effects for the model will include the treatment groups, randomization stratification factors [prostate cancer risk (low/intermediate), type of biopsy performed (mpMRI targeted/non mpMRI targeted)], age, race, and time since prostate cancer diagnosis. Additionally, a random effect of site will be included in the model.

The association between the survival time, log of time to disease progression, and survival probability, log negative log, will be investigated graphically by Cox proportional-hazards models. If the proportional hazards assumption is violated, appropriate remedial methods will be investigated and applied.

Data listings will be provided.

In addition to an overall analysis, the primary and secondary analyses will be repeated for pathological progression and therapeutic progression, individually.

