### **7.4.2 Analysis of Secondary Endpoints**

#### **7.4.2.1 Cancer Biopsy Incidence and Secondary Rise in PSA**

The incidence of negative biopsy for cancer and secondary rise in serum PSA will be summarized with frequencies and percentages at one and two years by treatment group, subgroups and overall.

Treatment comparisons will be performed using the exact binomial distribution as well as the normal approximation to the binomial distribution. Inferences will include 95% confidence intervals of the odds ratio for each endpoint between treatment groups at both Year 1 and Year 2 for biopsies and for each of Years 1 and 2 and end of study for PSA. Comparison between enzalutamide and AS will be evaluated by logistic regression using the treatment groups, randomization stratification factors [prostate cancer risk (low/intermediate), type of biopsy performed (mpMRI targeted/non mpMRI targeted)], age, race, and time since prostate cancer diagnosis as fixed effects and site and subject as random effects.

Time to PSA progression will be analyzed with the same methods as detailed for the primary endpoint analysis in Section 7.4.1.

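### PSA progression counts a 25% rise above nadir on its own, so PSA recovery after the planned one-year stop of enzalutamide is scored as progression in the Year 2, end-of-study and time-to-event comparisons

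*SAP*

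**What the plan says.** Section 3.1 defines PSA progression by three criteria joined by 'or': a rise relative to baseline, a rise relative to nadir, or an absolute increase. The last two read "25% above nadir or absolute increase". Section 6.1.2 repeats this structure. So does Section 6.4, in the sentence that begins "Rise in serum PSA is defined as". None of the three attaches a minimum absolute rise, a confirmation, or an on-drug or off-drug condition to the nadir criterion. The word 'secondary' in 'secondary rise' is not explained.

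Section 3.2 randomizes men to enzalutamide "once daily or to AS during the one year study treatment period". It continues: "Following the one year treatment period, all subjects will be followed for one additional year". On PSA it says: "Serum PSA will be measured at baseline and every 3 months during subsequent follow-up visits". The scheduled values at months 15, 18, 21 and 24 are therefore off drug in the enzalutamide arm.

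Section 7.4.2.1 compares the PSA-rise proportion between arms "for each of Years 1 and 2 and end of study for PSA", and adds: "Time to PSA progression will be analyzed with the same methods as detailed for the primary endpoint analysis in Section 7.4.1". Under Section 7.4.1, "subjects discontinuing therapy will not be censored until the time of study discontinuation". Stopping enzalutamide therefore does not end a man's follow-up for this endpoint.

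**The concern.** A nadir-referenced rule is sensitive to anything that lowers PSA and then lets it come back. In this design only one arm has a drug-induced nadir, and only that arm has a planned withdrawal. A man who ends the second year at exactly his entry PSA has no PSA evidence of worsening, yet he is an event if the drug had lowered his PSA enough. On active surveillance, the same criterion fires on ordinary variation around a stable level. The two arms are thus scored on different phenomena after month 12.

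At stake is the reading of the Year 2 and end-of-study odds ratios and of the hazard ratio for time to PSA progression. A reader of the report could take a cluster of events soon after month 12 as evidence that disease worsens in treated men. The SAP has no rule that resets the nadir at the planned stop, separates on-drug from off-drug rises, or analyses the PSA criteria one by one.

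**Working it through.** The SAP gives no event count, power or expected proportion for the PSA endpoint, so there is no planned figure to reproduce.

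**Step 1: threshold after suppression.** Let f be the fractional fall on drug. The nadir is (1 - f) x baseline, and the criterion fires at 1.25 x (1 - f) x baseline.

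- f = 20%: 1.25 x 0.80 = 1.00, so a return to baseline is an event.
- f = 50%: 1.25 x 0.50 = 62.5% of baseline.
- f = 80%: 1.25 x 0.20 = 25% of baseline.
- f = 90%: 1.25 x 0.10 = 12.5% of baseline.

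This step needs only the SAP's definition.

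**Step 2: timing, without measurement noise.** Assume half the remaining gap to baseline is recovered each quarter after month 12. True PSA k quarters later is then (1 - f x 0.5^k) x baseline. Dividing by the nadir (1 - f) gives:

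| Assumed fall | Month 15 | Month 18 | Month 24 |
|---|---|---|---|
| 30% | 0.85/0.70 = 1.21 | 0.925/0.70 = 1.32 | 0.981/0.70 = 1.40 |
| 50% | 0.75/0.50 = 1.50 | 0.875/0.50 = 1.75 | 0.969/0.50 = 1.94 |
| 80% | 0.60/0.20 = 3.00 | 0.80/0.20 = 4.00 | 0.95/0.20 = 4.75 |

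The 1.25 threshold is crossed at month 15 or 18 in every row, while PSA is still below its entry value.

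**Step 3: with noise.** Simulation of baseline plus eight quarterly values, lognormal within-man variation, the same flat underlying disease course in both arms, and the recovery pattern of step 2. Falls, recovery speed and CV are assumptions. Both criteria below are ratios, so the baseline PSA level does not matter. Share meeting each criterion at the month-24 visit, CV 10%:

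| | Enzalutamide (falls 30-80%) | Active surveillance |
|---|---|---|
| 25% above nadir | about 97-100% | 24% |
| 25% above baseline | about 3-4% | 6% |

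**Step 4: sensitivity.**

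- The active surveillance share meeting the nadir criterion at month 24 depends on the CV: about 1% at CV 5%, 24% at 10%, 47% at 15% and 60% at 20%.
- With falls of 50% or 80%, recovery of 25-75% of the remaining gap per quarter, CV 0-20% and underlying growth of 0 or 5% per year, the enzalutamide share at month 24 stays at 98-100%.
- At month 12, still on drug, the enzalutamide share (0-45% over those scenarios) is at or below the active surveillance share (0-52%). The ordering reverses only after the planned stop.

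**The case against.** **The two-year objective can still be answered.** A reader might infer that the two-year PSA question is lost. The documents do not support that. The baseline criterion is already part of the Section 3.1 definition and can be scored from PSA already collected. Section 7.5.2 also tabulates PSA values and change from baseline by arm at scheduled visits, so the report will show whether month-24 PSA is above entry level or merely back to it. This objection stands. What remains is that the planned between-arm tests do not use that information separately.

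**The size is not in the SAP.** It states neither the PSA fall on enzalutamide nor the recovery after stopping. A fall of less than 20% followed by return to baseline would not fire the rule, apart from noise. It is therefore an inference, not a documented fact, that nearly all treated men will be scored as progressed. This stands too. The 20% threshold itself is algebra.

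**Noise on active surveillance can be overstated.** If the proportion at two years means any qualifying value up to that time, 65%, 92% and 98% of stable men meet the nadir criterion at CVs of 10%, 15% and 20%. The SAP can equally mean status at the visit, which gives 24%, 47% and 60%. The larger figures hold only on the cumulative reading.

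**'Secondary rise' might require a prior fall.** This is possible, since the term is undefined. It would widen the asymmetry, because only one arm has a drug-induced fall.

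**Treatment-policy reading.** Time to PSA progression can be read as comparing a one-year course with surveillance. That comparison is legitimate, but its events would not then represent disease progression. The proportional-hazards check in Section 7.4.1 may reveal the step after month 12. It names no remedy, and it cannot re-score an event.

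**Weight.** This is one secondary endpoint of a study that Section 3.2 calls exploratory, and the primary endpoint does not use PSA.

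**Conclusion.** The concern holds for the Year 2 and end-of-study proportions and for the time-to-event curve after month 12. As defined, these would largely reflect recovery from drug withdrawal if enzalutamide lowers PSA by 20% or more and PSA recovers after the stop. Under the assumptions in step 3, the month-24 comparison is about 97-100% versus 24% on the nadir criterion and about 3-4% versus 6% on the baseline criterion, with no difference in underlying disease. The Year 1 comparison is essentially on drug and is not distorted by withdrawal.

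The wording of the rule and its consequence after a 20% fall are certain. The magnitude is conditional on suppression, recovery and within-man variation that the SAP does not give. The documents do not support saying that the objective is unanswerable, and they do not call for replacing the definition. The problem is separate from the wording difference between Section 6.4 and Section 3.1 on the baseline and absolute criteria. That difference also needs reconciling, but the nadir problem exists under either text.

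**What to change.** Keep the existing definition and add the following to Sections 6.4 and 7.4.2.1 before hard lock, which Section 1 allows:

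- A between-arm analysis of PSA rise referenced to pre-treatment baseline in both arms, using the baseline criterion of Section 3.1, for Year 1, Year 2, end of study and time to event. Interpretation after the treatment period should rest on this analysis.
- Results for each of the three PSA criteria separately.
- Nadir-based rises reported separately for the on-treatment period and for the period after end of treatment, with a statement that a nadir-only rise after the planned stop is not read as disease progression.

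Two stricter changes are not recommended. Requiring both 25% and 2 ng/mL above baseline makes the relative rise depend on entry PSA: 2/4 = 50% at 4 ng/mL and 2/8 = 25% at 8 ng/mL. Nothing in the SAP supports that choice. Mandatory confirmation at the next quarterly PSA cannot be applied to a month-24 rise, because visits then become six-monthly and follow-up ends when the last subject reaches month 24.

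The cost is one derived variable and one set of tables, with no new data. A baseline-referenced rule is slower to flag a true rise from a low on-drug nadir, but the retained nadir summary still shows it. While men are on drug the rule will seldom fire in the enzalutamide arm if PSA is suppressed, so its Year 1 result and the early part of its curve should be described as showing suppression.
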